Appendix C. Karnofsky Performance Status Scores

%	Karnofsky Performance Status
100	Normal; no complaints; no evidence of disease.
90	Able to carry on normal activity; minor signs or symptoms of disease.
80	Normal activity with effort; some signs or symptoms of disease.
70	Care for self. Unable to carry on normal activity or do active work.
60	Requires occasional assistance but is able to care for most of his or her needs.
50	Requires considerable assistance and frequent medical care.
40	Disabled, requires special care and assistance.
30	Severely disabled; hospitalization is indicated though death not imminent.
20	Hospitalization necessary; very sick; active supportive treatment necessary.
10	Moribund; fatal processes progressing rapidly.
0	Dead.

Appendix D. Non-Investigational Treatments for cGVHD

Medications or procedures not considered to be investigational for the treatment of chronic graft-versus-host disease.

Cellcept
Cyclosporine
Etanercept or other FDA-approved TNF α inhibitors
Extracorporeal photophoresis (ECP)
Imatinib
Methotrexate
Pentostatin
Rituximab
Sirolimus
Tacrolimus

Appendix E. Lee cGVHD Symptom Scale

Identification (Name): _____

Date: _____

chronic GVHD Symptom Scale

By circling one (1) number per line, please indicate how much you have been bothered by the following problems in the past month:

SKIN:	Not at all	Slightly	Moderately	Quite a bit	Extremely
1. Abnormal skin color.....	0	1	2	3	4
2. Rashes.....	0	1	2	3	4
3. Thickened skin.....	0	1	2	3	4
4. Sores on skin.....	0	1	2	3	4
5. Itchy skin.....	0	1	2	3	4
EYES AND MOUTH:	Not at all	Slightly	Moderately	Quite a bit	Extremely
6. Dry eyes.....	0	1	2	3	4
7. Need to use eye drops frequently..	0	1	2	3	4
8. Difficulty seeing clearly.....	0	1	2	3	4
9. Need to avoid certain foods due to mouth pain.....	0	1	2	3	4
10. Ulcers in mouth.....	0	1	2	3	4
11. Receiving nutrition from an intravenous line or feeding tube....	0	1	2	3	4
BREATHING:	Not at all	Slightly	Moderately	Quite a bit	Extremely
12. Frequent cough.....	0	1	2	3	4
13. Colored sputum.....	0	1	2	3	4
14. Shortness of breath with exercise..	0	1	2	3	4
15. Shortness of breath at rest.....	0	1	2	3	4
16. Need to use oxygen.....	0	1	2	3	4

EATING AND DIGESTION:		Not at all	Slightly	Moderately	Quite a bit	Extremely
17.	Difficulty swallowing solid foods....	0	1	2	3	4
18.	Difficulty swallowing liquids.....	0	1	2	3	4
19.	Vomiting.....	0	1	2	3	4
20.	Weight loss.....	0	1	2	3	4
MUSCLES AND JOINTS:		Not at all	Slightly	Moderately	Quite a bit	Extremely
21.	Joint and muscle aches.....	0	1	2	3	4
22.	Limited joint movement.....	0	1	2	3	4
23.	Muscle cramps.....	0	1	2	3	4
24.	Weak muscles.....	0	1	2	3	4
Energy:		Not at all	Slightly	Moderately	Quite a bit	Extremely
25.	Loss of energy.....	0	1	2	3	4
26.	Need to sleep more/take naps.....	0	1	2	3	4
27.	Fevers.....	0	1	2	3	4
MENTAL AND EMOTIONAL:		Not at all	Slightly	Moderately	Quite a bit	Extremely
28.	Depression.....	0	1	2	3	4
29.	Anxiety.....	0	1	2	3	4
30.	Difficulty sleeping.....	0	1	2	3	4

Source:

http://www.uniklinikum-regensburg.de/imperia/md/content/kliniken-institute/haematologie-onkologie/gvhd/deutsch/lee-symptom_scale.pdf

Appendix F. Chronic GVHD Activity Assessment – Clinician**Guidelines for completing the Chronic GVHD Activity Assessment – Clinician Form:**

EYES- If Schirmer's Tear test is not performed please complete the NIH eye score.

LUNGS-Complete full PFTs if possible but FEV1 is required.

--If FEV1 is normal at baseline, repeat assessment not required unless progression is suspected. Complete NIH lung score in place of FEV1 at each visit.

--If FEV1 is abnormal at baseline then reassessment Q12 weeks is required.

GRIP STRENGTH-Not necessary to complete

2 MIN WALK TEST-Complete only at baseline

[figure not shown]

RANGE OF MOTION—Complete photographic ROM score and NIH joint/fascia score

** If a change in score is considered to be due to a cause other than cGVHD please note and mark NE (not evaluable) for cGVHD score.

FORM A

Current Patient Weight: _____ **Today's Date:** _____ **MR#/Name:** _____

CHRONIC GVHD ACTIVITY ASSESSMENT- CLINICIAN

[figure not shown]
Component	Findings		Scoring (see skin score worksheet)						
	Erythematous rash of any sort		% BSA (max 100%)						
	Moveable sclerosis		% BSA (max 100%)						
	Non-moveable sclerosis (hidebound/non-pinchable) or subcutaneous sclerosis/fasciitis		% BSA (max 100%)						
	Ulcer(s): select the largest ulcerative lesion, and measure its largest dimension in cm and mark location of ulcer		Location: _____ Largest dimension: _____ cm						
Eyes Bilateral Schirmer's Tear Test (without anesthesia) in persons 9 years or older	Right Eye: _____ mm of wetting		Left Eye: _____ mm of wetting						
Mouth 	Mucosal change	No evidence of cGVHD	Mild	Moderate	Severe				
	Erythema	None	0	Mild erythema or moderate erythema (<25%)	1	Moderate (≥25%) or Severe erythema (<25%)	2	Severe erythema (≥25%)	3
	Lichenoid	None	0	Hyperkeratotic changes(<25%)	1	Hyperkeratotic changes(25-50%)	2	Hyperkeratotic changes (>50%)	3
	Ulcers	None	0	None	0	Ulcers involving (≤20%)	3	Severe ulcerations (>20%)	6
	Mucoceles*	None	0	1-5 mucoceles	1	6-10 scattered mucoceles	2	Over 10 mucoceles	3
					*Mucoceles scored for lower labial and soft palate only				
							Total score for all mucosal changes		
Blood Counts	Platelet Count	ULN	Total WBC	ULN	% Eosinophils				
	K/uL	K/uL	K/uL	K/uL	%				
Liver Function Tests	Total serum bilirubin	ULN	ALT	ULN	Alkaline Phosphatase				
	mg/dL	mg/dL	U/L	U/L	U/L				
					U/L				

Gastrointestinal-Upper • Early satiety OR • Anorexia OR • Nausea & Vomiting	0= no symptoms 1=mild, occasional symptoms, with little reduction in oral intake during the past week 2=moderate, intermittent symptoms, with some reduction in oral intake during the past week 3=more severe or persistent symptoms throughout the day, with marked reduction in oral intake, on almost every day of the past week																								
Gastrointestinal-Esophageal • Dysphagia OR • Odynophagia	0= no esophageal symptoms 1=Occasional dysphagia or odynophagia with solid food or pills during the past week 2=Intermittent dysphagia or odynophagia with solid foods or pills, but not for liquids or soft foods, during the past week 3=Dysphagia or odynophagia for almost all oral intake, on almost every day of the past week																								
Gastrointestinal-Lower = • Diarrhea	0= no loose or liquid stools during the past week 1= occasional loose or liquid stools, on some days during the past week 2=intermittent loose or liquid stools throughout the day, on almost every day of the past week, without requiring intervention to prevent or correct volume depletion 3=voluminous diarrhea on almost every day of the past week, requiring intervention to prevent or correct volume depletion																								
Lungs • Bronchiolitis Obliterans	Pulmonary Function Tests with Diffusing Capacity (attach report for person> 5 yrs old)	FEV-1 % Predicted	Single Breath DLCO (adjusted for hemoglobin) % Predicted																						
Health Care Provider Global Ratings: In your opinion, do you think that this patient's chronic GVHD is mild, moderate or severe? 0=none 1= mild 2=moderate 3=severe	Where would you rate the severity of this patient's chronic GVHD symptoms on the following scale, where 0 is cGVHD symptoms that are not at all severe and 10 is the most severe cGVHD symptoms possible: 
 
 0	1	2	3	4	5	6	7	8	9	10	
 
 cGvHD symptoms not at all severe	Most severe cGvHD symptoms possible	
 
		0	1	2	3	4	5	6	7	8	9	10	cGvHD symptoms not at all severe						Most severe cGvHD symptoms possible					Over the past month would you say that this patient's cGVHD is +3= Very much better +2= Moderately better +1= A little better 0= About the same -1=A little worse -2=Moderately worse -3=Very much worse
0	1	2	3	4	5	6	7	8	9	10															
cGvHD symptoms not at all severe						Most severe cGvHD symptoms possible																			
Functional Performance (in persons >4 years old) • Walk Time • Grip Strength	Total Distance Walked in 2 Minutes: Number of laps: _____ (x 50 feet) + final partial lap: _____ feet = _____ feet walked in 2 minutes	Grip Strength (Dominant Hand) Trial #1 Trial #2 Trial #3 psi psi psi		Range of Motion: o Not performed o Physical Therapy Report Attached																					
	Score	Lansky Performance Status Scale Definitions (circle from 0-100) (persons < 16 years old)		Karnofsky Performance Status Scale Definitions (circle from 0-100) (persons 16 years or older)																					
100	Fully active, normal		Normal no complaints; no evidence of disease																						
90	Minor restrictions in physically strenuous activity		Able to carry on normal activity; minor signs or symptoms of disease																						
80	Active, but tires more quickly		Normal activity with effort; some signs or symptoms of disease																						
70	Both greater restriction of and less time spent in play activity		Cares for self; unable to carry on normal activity or to do active work																						
60	Up and around, but minimal active play; keeps busy with quieter activities		Requires occasional assistance but is able to care for most personal needs																						
50	Gets dressed but lies around much of the day, no active play but able to participate in all quiet play and activities		Requires considerable assistance and frequent medical care																						
40	Mostly in bed; participates in quiet activities		Disabled; requires special care and assistance																						
30	In bed; needs assistance even for quiet play		Severely disabled; hospital admission is indicated although death not imminent																						
20	Often sleeping; play entirely limited to very passive activities		Very sick; hospital admission necessary; active supportive treatment necessary																						
10	No play; does not get out of bed		Moribund; fatal processes progressing rapidly																						
0	Unresponsive		Dead																						

Source: <http://asbmt.affiniscap.com/associations/11741/files/ResponseCriteriaAPPENDIXAFormA.pdf>

	Score 0	Score 1	Score 2	Score 3
JOINTS AND FACIA	 No Symptoms	 Mild tightness of arms or legs, normal or mild decreased range of motion(ROM) AND not affecting ADL	 Tightness of arms or legs OR joint contractures, erythema thought due to fasciitis, moderate decrease ROM AND mild to moderate limitation of ADL	 Contractures WITH significant decrease of ROM AND significant limitation of ADL (unable to tie shoes, button shirts, dress self etc)
 Abnormality present but explained entirely by non-GVHD documented cause (specify): _____				
	Score 0	Score 1	Score 2	Score 3
EYES	 No symptoms	 Moderate dry eye symptoms not affecting ADL (requirement of lubricant eye drops \leq 3 x per day)	 Moderate dry eye symptoms partially affecting ADL, (requiring eye drops > 3 x per day or punctual plugs), WITHOUT new vision impairment due to KCS	 Severe dry eye symptoms significantly affecting, ADL (special eyeware to relieve pain) OR unable to work because of ocular symptoms OR loss of vision due to KCS
 Abnormality present but explained entirely by non-GVHD documented cause (specify): _____				
	Score 0	Score 1	Score 2	Score 3
LUNGS	 No symptoms	 Mild symptoms (shortness of breath after climbing one flight of steps)	 Moderate symptoms (shortness of breath after walking on flat surface)	 Severe symptoms (shortness of breath at rest; requiring O ₂)
 Abnormality present but explained entirely by non-GVHD documented cause (specify): _____				

RANGE OF MOTION:

Not done

Not done

Not done

Appendix G. Chronic GVHD Activity Assessment – Patient Self Report

FORM B Today's Date: _____ MR#/Name: _____

CHRONIC GVHD ACTIVITY ASSESSMENT-PATIENT SELF REPORT

Symptoms	Please rate how severe the following symptoms have been in the last seven days. Please fill in the circle below from 0 (symptom has not been present) to 10 (the symptom was as bad as you can imagine it could be) for each item.										
	Not Present						As Bad As You Can Imagine				
	0	1	2	3	4	5	6	7	8	9	10
Your skin itching at its WORST?											
Your mouth dryness at its WORST?											
Your mouth sensitivity at its WORST?											
Eyes	What is your main complaint with regard to your eyes?										
	Please rate how severe is this eye symptom, between 0 (not at all severe) and 10 (most severe):						0 1 2 3 4 5 6 7 8 9 10				
Vulvovaginal Symptoms (females only)	Do you have any burning, pain or discomfort in the area of your vagina, vulva or labia?						 Yes  No  Not applicable				
	Do you have any discomfort or pain with sexual intercourse?										

Patient Global Ratings:

1. Overall, do you think that your chronic graft versus host disease is mild, moderate or severe?

0= none
1= mild
2=moderate
3=severe

2. Please circle the number indicating how severe your chronic graft versus host disease symptoms are, where 0 is cGVHD symptoms that are not at all severe and 10 is the most severe chronic GVHD symptoms possible.

0	1	2	3	4	5	6	7	8	9	10
cGVHD symptoms not at all										Most severe cGVHD severe symptoms possible

3. Compared to a month ago, overall would you say that your cGVHD symptoms are:+3= Very much better
+2= Moderately better
+1=A little better
0= About the same
-1=A little worse
-2=Moderately worse
-3=Very much worse**Attach copies of:****Adults (persons 18 years or older):**

- Lee cGVHD Symptom Scale
- Human Activity Profile
- SF-36 v.2
- FACT-BMT

Children/Adolescents (persons 17 years or younger):

- Lee cGVHD Symptom Scale (persons 8-12 years old may complete with help of the health care professional)
- ASK - Activities Scale for Kids
- CHRIs - Generic and Disease Specific Inventory

Source: <http://asbmt.affiniscap.com/associations/11741/files/ResponseCriteriaAPPENDIXBFormB.pdf>

Appendix H. Response Criteria for Partial Response and Progression in cGVHD**Proposed calculations for partial response in chronic GVHD**

Organ and Starting Score or Value	Partial Response Criterion*
Skin (percent of body surface)	
> 50	$e/s \leq 0.5$ and $e > 0$
25 – 50	$s - e \geq 25$ and $e > 0$
< 25	only CR; no PR possible
Eye (mm Schirmer's test)	
< 5 mm	$e - s \geq 5$ mm and $e < \text{LLN}$
5 – 10 mm	only CR; no PR possible
Mouth (15-point Schubert scale)	
≥ 8	$e/s \leq 0.5$ and $e > 0$
4 – 7	$s - e \geq 4$ and $e > 0$
< 4	only CR; no PR possible
Platelet count	$e - s \geq 100,000/\text{uL}$ and $e < \text{LLN}$
Gastrointestinal (and other 0 – 3 scales)†	
3	$e = 1$ or 2
2	$e = 1$
1	only CR; no PR possible
Liver function tests (ALT, alkaline phosphatase and bilirubin) and eosinophil count	
$\geq 3 \times \text{ULN}$	$e/s \leq 0.5$ and $e > \text{ULN}$
< 3 x ULN	only CR; no PR possible

* s, starting score or value; e, ending score or value; ULN, upper limit of normal; LLN, lower limit of normal

† The proposed response criterion could be appropriate for shorter-term phase II studies. For longer-term pivotal phase III studies, a 1-point change might not be sufficient for PR.

Examples :

1. Skin: start score = 85, end score = 30; $e/s = 30/85 = 0.35 = \text{PR}$
2. Skin: start score = 65, end score = 45; $e/s = 45/65 = 0.75 = \text{not PR}$
3. Skin: start score = 45, end score = 15; $s - e = 30 = \text{PR}$
4. Skin: start score = 30, end score = 15; $s - e = 15 = \text{not PR}$

Appendix H. Response Criteria for Partial Response and Progression in cGVHD (Cont'd)**Proposed calculations for progression in chronic GVHD**

Organ and Starting Score or Value	Progression Criterion*
Skin (percent of body surface)	$e - s \geq 25$
Eye	$s - e \geq 5 \text{ mm}$
Mouth (15-point Schubert scale)	$e - s \geq 3$
Platelet count	$s - e \geq 50,000/\text{uL}$ and $e < \text{LLN}$
Gastrointestinal (and other 0 – 3 scales)	$e - s \geq 1$
Liver (ALT, alkaline phosphatase and bilirubin), eosinophil count	
$s \geq 3 \times \text{ULN}$	$e - s \geq 3 \times \text{ULN}$
$s < 3 \times \text{ULN}$	$e - s \geq 2 \times \text{ULN}$
Lungs (12-point Lung Function Scale)	$e - s \geq 3^\dagger$

****Score changes from 0 to 1 are not considered progression.**

*s, starting score or value; e, ending score or value; ULN, upper limit of normal

† If the starting lung function score is ≥ 10 , progression is defined as $\geq 5\%$ decrease of FEV1 in two tests measured at least 2 weeks apart. This time interval was selected because these syndromes can progress rapidly.

http://asbmt.affiniscape.com/associations/11741/files/ResponseCriteriaAPPENDIXC_DCCalculations.pdf

Appendix I. Guidelines for Chronic GVHD Activity Assessment – Clinician (FORM A)

Any measure that is normal and does not have cGVHD involvement at Day 1 = NE (not evaluable), remains NE unless criteria for PD is met.

Any measure that changes but is not felt to be related to cGVHD should be marked as NE. Organs with more than one component will have each component evaluated, and then an organ score will be assigned.

Overall cGVHD assessment: SD: no PR, no PD, no CR

PR: if no PD and ≥ 1 PR

PD: if ≥ 1 PD

CR: all CR

Measures	Individual Response*	Overall organ response
Skin (percent of body surface) Body surface area of erythematous rash		NE: no cGVHD SD: no PR, no PD, no CR
Skin Body surface area of moveable sclerosis		PR: if no PD and ≥ 1 PR
Skin Body surface area of non-moveable sclerosis		PD: if ≥ 1 PD CR: all CR
Eyes – Right eye Schirmer Tear Test (mm wetting)		NE: no cGVHD
Eyes – Left Eye Schirmer Tear Test (mm wetting)		SD: no PR, no PD, no CR PR: if no PD and ≥ 1 PR PD: if ≥ 1 PD CR: all CR
Mouth Mucosal change (Scores range from 0-15)		NE: no cGVHD SD: no PR, no PD, no CR PR PD CR
Blood Counts Platelet count and absolute eosinophil count		NE: no cGVHD SD: no PR, no PD, no CR PR: if no PD and ≥ 1 PR PD: if ≥ 1 PD CR: all CR
Liver Function Tests ALT, total serum bilirubin and alkaline phosphatase		NE: no cGVHD SD: no PR, no PD, no CR PR: if no PD and ≥ 1 PR PD: if ≥ 1 PD CR: all CR
GI – Upper		NE: no cGVHD SD: no PR, no PD, no CR
GI – Esophageal		PR: if no PD and ≥ 1 PR
GI – Lower		PD: if ≥ 1 PD CR: all CR
Lung response Pulmonary Function Tests with Diffusing Capacity, FEV1 and DLCO		NE: no cGVHD SD: no PD PD No possible PR or CR
Overall cGVHD Response		SD: no PR, no PD, no CR PR: if no PD and ≥ 1 PR PD: if ≥ 1 PD CR: all CR

*See [Appendix H](#) for individual response

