7.2. Efficacy Evaluations

7.2.1. NIH Response Criteria (see [Appendix F](#) and [Appendix G](#))

All subjects in the study will have their response assessed using the NIH cGVHD Response assessment ([Pavletic 2006](#); [Measurement of Therapeutic Response, ASBMT Web site](#)) at baseline, at week 5, and after every 12 weeks of therapy. Response will be determined by the following criteria:

1. Complete Response – Complete resolution of all reversible manifestations of cGVHD. Irreversible manifestations will be defined by NIH consensus criteria ([Pavletic 2006](#)) (eg, ocular xerosis, esophageal stricture, and bronchiolitis obliterans).
2. Partial Response – At least a 25% absolute or 50% relative change (whichever is greater) when comparing start and end measurements in one cGVHD domain without worsening in the other domains ([Appendix H](#)).
3. Stable Disease – No worsening in baseline cGVHD manifestations.
4. Progressive Disease – Worsening in any one cGVHD domain by at least an absolute change of 25% from baseline unless baseline values are within 25% of the scale used to score cGVHD. In addition, a new cGVHD manifestation also counts as progression ([Appendix H](#)).

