10.2. Endpoints

10.2.1. Primary Endpoints

Phase 1b:

Safety and Tolerability

Drug toxicity will be described and graded according to [CTCAE v. 4.03](#) criteria. Dose limiting toxicities are defined in [Section 5.2.2](#). Only toxicities which occur during the first 28 days on ibrutinib will count towards the assessment of DLTs.

Toxicities which occur after the first 28 days for Phase 1b subjects will be described and graded according to [CTCAE v. 4.03](#) criteria and presented in tabulated form. This will also be performed for subjects enrolled in the Phase 2 portion of the study.

Phase 2:

The primary efficacy endpoint is the best overall cGVHD response rate. Best overall cGVHD response rate is defined the proportion of subjects who achieve a NIH-defined complete response or partial response.

Please refer to [Section 7.2.1](#) for the definition of overall cGVHD response.

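### Appendix I does not let a fully cleared organ count toward overall partial response, which conflicts with Section 7.2.1, the definition to which the primary endpoint points

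*Protocol*

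**What the plan says.** **Appendix I (guideline for Form A).** The overall rule begins "Overall cGVHD assessment: SD: no PR, no PD, no CR". Overall PR needs at least one PR and no PD, any PD makes the visit PD, and CR needs every organ to be CR. The same four lines apply inside organs with several measures: "Organs with more than one component will have each component evaluated, and then an organ score will be assigned". The lung row adds "No possible PR or CR".

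**Appendix H (organ thresholds).** Every PR row stops short of normalisation. Skin and mouth need an end score above 0, and 0–3 scales need an end score of at least 1. Schirmer and platelets must still be below the lower limit of normal; liver tests and eosinophils must still be above the upper limit. Low starting values are marked "only CR; no PR possible".

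**Section 7.2.1.** CR is "Complete resolution of all reversible manifestations of cGVHD". PR is a change of at least the larger of 25% absolute and 50% relative, "when comparing start and end measurements in one cGVHD domain without worsening in the other domains", with Appendix H cited. The sentence itself sets no upper limit on the improvement.

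**Endpoint sections.** Section 10.2.1 refers the reader to Section 7.2.1 "for the definition of overall cGVHD response". SAP 5.1 uses investigator assessments under the 2005 NIH criteria with two modifications: one on non-evaluable findings, one on score changes from 0 to 1. Neither says how an organ CR combines with an organ SD.

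**The concern.** Because Appendix H makes a cleared organ CR and not PR, and Appendix I asks for an organ PR, clearing one organ while another stays stable does not produce an overall response under Appendix I. A partial improvement in the same organ does. The larger benefit ranks below the smaller one, and it does so in the two manifestations that qualify subjects for entry (rash and mouth).

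Three analyses could be touched. Best overall response is the primary endpoint. Duration of response (DOR) starts at the first documented response. Sustained response is the only secondary endpoint with a formal test (SAP 5.2). The study is open-label and investigator-assessed, so the rule should be settled before the data are reviewed.

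**Working it through.** The plan states no figure on this point, so the check compares the rules and works examples.

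**Inputs**
- Entry: rash >25% BSA or mouth score >4 (Protocol 4.1, criterion 5).
- Scale maxima: mouth 15, skin 100% BSA (Appendices H and I).
- Section 7.2.1 threshold: change ≥ max(25% of scale, 50% of start). Reading 25% absolute as a quarter of the scale is my interpretation. Appendix H supports it: 25 points for skin starts of 25–50, and 4 points for mouth starts of 4–7 (0.25 × 15 = 3.75).
- Visit target days 29, 85, 169, 253 (SAP Appendix 8.1); sustained-response bound 137 days (SAP 5.2.1).

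**Step 1: which visits are affected.** With k involved organs, each CR, PR, SD or PD, there are 4^k combinations. Those made only of CR and SD, with both present, number 2^k − 2: 2 of 16, 6 of 64 and 14 of 256 for k = 2, 3, 4. Under Appendix I these are uncategorised on the literal reading and SD on the residual reading. They are counts of patterns, not expected frequencies. The same happens within an organ, for example rash cleared with moveable sclerosis unchanged.

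**Step 2: does clearance meet the 7.2.1 threshold?** With end score 0 the change equals the start s.
- Mouth: s ≥ max(3.75, 0.5s) holds for s ≥ 3.75, so for all 11 eligible starts (5–15).
- Skin: s ≥ max(25, 0.5s) holds for s ≥ 25, so for all 75 eligible whole-percent starts (26–100).

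**Step 3: ranking, mouth start 12, skin stable.** The 7.2.1 threshold is max(3.75, 6) = 6.

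| End score | Change | Appendix H, mouth | Appendix I, overall | 7.2.1, general wording |
|---|---|---|---|---|
| 5 | 7 | PR (5/12 = 0.42) | PR | PR |
| 0 | 12 | CR | none, or SD | at least PR |

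**Step 4: two constructed subjects, both starting at mouth 12 and skin 40%.**
- *Missed responder.* Mouth is 0 at every visit and skin stays at 40%. Appendix I never gives a response; 7.2.1 gives PR at all four visits. One assessed visit at an intermediate mouth score such as 5 would make the subject a responder under both.
- *Later dating.* Mouth is 0 at every visit; skin is 40, 40, 10, 65. Skin is SD, SD, PR (40 − 10 = 30 ≥ 25) and PD (65 − 40 = 25). Appendix I gives its first response on Day 169; 7.2.1 gives PR on Days 29, 85 and 169. Both give PD on Day 253. DOR is 253 − 169 = 84 days against 253 − 29 = 224 days, so onset is 140 days later under Appendix I. The 137-day bound is missed under Appendix I and met under 7.2.1. Counting only to the last response visit gives the same answer (0 against 140 days).

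**Step 5: lung.** With lung SD and every other organ CR, Appendix I cannot give CR, because of its lung row, or PR. Section 7.2.1 limits CR to reversible manifestations and names bronchiolitis obliterans as an irreversible one, so it could call the visit CR.

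**Scale only.** The exact lower 95% limit is the 0.025 quantile of Beta(r, 41 − r) for r of 40: 24.9% at r = 16 and 27.0% at r = 17. One subject decides the 25% rule only if the total lies at that margin.

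**The case against.** A reader might infer that the protocol leaves these visits with no category at all. The documents do not establish that. The single-measure Mouth row of Appendix I uses the same SD wording, and there it can only mean a result that is none of the other three. Read that way at overall level, the visit is SD. Nor is Appendix I the only rule that combines organs, since Section 7.2.1 also works across domains. What stands is that SD is still a non-response where the general wording of 7.2.1 gives PR.

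The strongest defence is that the governing definition is already named. Section 10.2.1 points to 7.2.1, and 7.2.1 cites Appendices F, G and H. No operative section cites Appendix I for response; the body text mentions it only in exclusion criterion 20, on CYP3A inhibitors. This is correct and limits the harm to cases where Appendix I is followed. But it is the protocol's guideline for the investigator's form, and the primary endpoint rests on investigator assessments.

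It is also fair to say that 7.2.1 is less clean than its sentence suggests. It cites Appendix H, whose PR rows exclude normalisation, so part of the tension lies between those two texts. That is a further reason to state the rule.

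Finally, SAP 5.2.1 tolerates SD visits between responses. On the residual reading this protects some subjects, but not one whose clearance comes before the first labelled response.

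**Conclusion.** The point stands as a conflict between stated rules that should be resolved. Under Appendix I a cleared organ does not count toward overall PR, on either reading of its SD line. Under the general wording of 7.2.1 it does, for every eligibility-level mouth or rash start. This rests on reading 25% absolute as a quarter of the scale.

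A reader might go further and infer that the primary endpoint is undefined, or that the response rate is understated by a calculable amount. Neither follows. If 7.2.1 is applied, nothing is lost, and the documents give no basis for the number of affected subjects, which may be zero. The trajectories show what can happen, not how often. SAP 5.1 also relies on the 2005 NIH criteria, which are not in the documents, so whether that source settles the mixed visit cannot be checked here.

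**What to change.** 1. In Appendix I, at overall level and within multi-component organs, and in SAP 5.1, state: *PR: no PD, not all CR, and at least one organ (or component) with PR, or with CR whose improvement meets the Section 7.2.1 threshold. SD: all other visits without PD.*
2. State that the normalisation limits in Appendix H only separate organ PR from organ CR, and do not remove a cleared organ from overall response.
3. Record two decisions before data review. The first is how CR from low starts counts. The threshold treats these unevenly: mouth 3 to 0 is a change of 3, below 3.75, whereas a 0–3 item going from 1 to 0 is a change of 1, above 0.75. The second is how CR counts in measures without a fixed scale maximum (Schirmer, platelets, liver tests, eosinophils), where a quarter of the scale cannot be computed.
4. Reconcile the lung row with the restriction of CR to reversible manifestations in 7.2.1.
5. Use one per-visit category for best response, sustained response and DOR.

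The cost is wording in Appendix I and SAP 5.1, one derivation rule and the recorded decisions. No new data or visits are needed.
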